**Table 3-1 Voruciclib Dose Escalation Levels Prior to Amendment 7**

| Cohort/Dose Level | Daily Dose |
|-------------------|------------|
| 1                 | 50 mg      |
| 2                 | 100 mg     |
| 3                 | 150 mg     |
| 4                 | 200 mg     |
| 5                 | 250 mg     |

[figure not shown]
As of Amendment 7, dosing will be modified to test the safety and efficacy of voruciclib administered on an IS. Because the mBED and the recommended phase 2 dose (RP2D) will be assessed independently for subjects with AML and B-cell malignancies, dose and regimen evaluations will be conducted in each of these disease groups separately by opening the next cohort in each disease group as determined by the Study Review Committee (SRC). In order to differentiate disease-specific cohorts, subjects with AML will be designated as Cohorts 6a-11a, and subjects with B-cell malignancies will be designated as Cohorts 6b-11b (see Table 3-2).

**Table 3-2 Voruciclib Dose Escalation Levels in Amendment 7**

| Cohort Dose Level | Dose Schedule              |
|-------------------|----------------------------|
| 6a, b             | 100 mg IS 2w,2w |
| 7a, b             | 150 mg IS 2w,2w |
| 8a, b             | 200 mg IS 2w,2w |
| 9a, b             | 100 mg IS 1w,3w |
| 10a, b            | 150 mg IS 1w,3w |
| 11a, b            | 200 mg IS 1w,3w |

The dose escalation scheme for IS is detailed in Figure 3-2. The total number of cohorts will depend upon the incidence of DLTs.

**Figure 3-1 Dose Escalation Scheme for IS**

\* Patients with AML and B-Cell malignancies will be enrolled separately into this scheme.

Subjects with AML will be designated as Cohorts Xa, and subjects with B-cell malignancies will be designated as Cohorts Xb.

Once the RP2D has been declared in AML group, an expansion cohort of 12 subjects will be enrolled to further characterize the Safety and efficacy of this dose and schedule in AML.

Dose escalation will be allowed after 3 subjects have completed 1 cycle with no reported DLT, or 6 subjects have completed 1 cycle with no more than 1 DLT. Escalation to the next higher

dose level will depend on demonstrated safety, tolerability and DLT as defined in the study protocol (Section 4.4) and after approval by the SRC.

Subjects may continue to receive voruciclib while there is evidence of clinical benefit and acceptable toxicity as judged by the Investigator. The Investigator may increase the voruciclib dose level above the initial dose assigned at enrollment after the SRC has authorized opening enrollment at a new dose level, and after consultation with the Medical Monitor. Subjects whose voruciclib dose is increased to the next dose level will not count toward the assessment of DLTs at the higher dose level.

Because enrollment will be conducted independently in subjects with AML and B-cell malignancies, it is possible the voruciclib dose and/or schedule under evaluation at any time point may be different in the 2 groups.

As of Amendment 11, subsequent to determination of the safe and mBED of voruciclib monotherapy in AML subjects, the combination of voruciclib with venetoclax will be evaluated in subjects with relapsed and/or refractory AML.

The combination cohorts, beginning at Cohort 12 dose level of voruciclib in combination with venetoclax on an IS2w,2w dosing schedule, will be enrolled as defined in Table 3-3:

**Table 3-3 Cohorts with Combination Voruciclib + Venetoclax in Amendment 12**

| Cohort Dose Level | Doses and Schedule   |
|--------------------------|---|
| 12                       | voruciclib 50 mg QOD, administered IS 2w,2w + venetoclax administered QD × 28 days |
| 13                       | voruciclib 50 mg QD, administered IS 2w,2w + venetoclax administered QD × 28 days  |
| 14                       | voruciclib 100 mg QD, administered IS 2w,2w + venetoclax administered QD × 28 days |
| 15                       | voruciclib 150 mg QD, administered IS 2w,2w + venetoclax administered QD × 28 days |
| 16                       | voruciclib 200 mg QD, administered IS 2w,2w + venetoclax administered QD × 28 days |
| 17                       | voruciclib 250 mg QD, administered IS 2w,2w + venetoclax administered QD × 28 days |
| 18                       | voruciclib 300 mg QD, administered IS 2w,2w + venetoclax administered QD × 28 days |
| 19                       | voruciclib 350 mg QD, administered IS 2w,2w + venetoclax administered QD × 28 days |
| 20                       | voruciclib 150 mg QD, administered IS 3w,1w + venetoclax administered QD × 28 days |

Dose escalation proceeds until a real-time assessment of clinical and PK parameters by the SRC establishes the safe and mBED for voruciclib in combination with venetoclax. More specifically, a voruciclib dose in combination with venetoclax that meets the following criteria:

- DLT not to exceed 1 in 6 subjects, overall response rate (ORR)  $\geq 30\%$ , as compared to historical ORR of 19% with 400-800 mg venetoclax alone in relapsed/refractory AML, and
- Trough plasma concentration of 1 to 1.5  $\mu\text{M}$ , concentrations shown to be synergistic in combination with venetoclax in preclinical models.

Once the safe and mBED of voruciclib in combination with venetoclax is identified by the SRC, which could be a dose less than 350 mg, dose escalation will stop. The subjects still actively dosing in the prior cohort may have their dose escalated to the next dose level after completing Cycle 1 (intra subject dose escalation). Subjects may continue to receive voruciclib plus venetoclax while there is evidence of clinical benefit (partial remission [PR] or better) by the end of Cycle 6 and acceptable toxicity as judged by the Investigator.

### **3.1.2 Maximum Tolerated Dose (MTD), Minimum Biologically Effective Dose (mBED) and Recommended Phase 2 Dose (RP2D)**

With respect to voruciclib monotherapy, for each disease group and schedule (continuous,  $\text{IS}_{2\text{w},2\text{w}}$ ,  $\text{IS}_{1\text{w},3\text{w}}$ ), an MTD of voruciclib will be defined as the highest dose at which  $<2$  of 6 subjects experience a DLT.

With respect to voruciclib + venetoclax combination therapy, an MTD will be defined as the highest dose cohort level at which  $<2$  of 6 subjects experience a DLT.

The study may not be sufficient to determine the RP2D and schedule of voruciclib therapy in hematologic malignancies. It will evaluate the safety, efficacy, and the safe and mBED of voruciclib therapy. The safe and mBED and schedule will be determined based on safety and tolerability over two or more cycles, achievement of voruciclib blood levels that have demonstrable activity in non-clinical studies, and/or additional evidence of biologic or clinical activity. The safe and mBED may be different in AML and B-cell malignancies for monotherapy, and may be the same or lower than the MTD.

### **3.1.3 Dose Expansion Plan**

Once the safe and mBED of voruciclib has been declared in the group of subjects with AML of voruciclib monotherapy and/or voruciclib + venetoclax combination therapy, an expansion cohort of 6 subjects with AML of voruciclib monotherapy, or an expansion cohort of 12 subjects with AML of voruciclib + venetoclax combination therapy, will be enrolled to further characterize the safety, efficacy, PK and effect on biomarkers of this dose level and schedule in AML.

To date, there is no plan to open a dose expansion cohort in B-cell malignancies.

### **3.1.4 Subject Replacement**

Subjects who discontinue study therapy prior to completing Cycle 1 (Day 28) for reasons other than the development of a DLT will be replaced. Subjects who miss one or more doses for reasons other than a DLT, must receive at least 75% of the total planned dose in Cycle 1 to be assessed for a DLT. Subjects with no DLT who fail to receive at least 75% of the planned Cycle 1 voruciclib dose will be replaced.

For Cohort 12, subjects must receive 100% of Cycle 1 doses (i.e., all 6 doses) to be DLT evaluable; subjects with no DLT who fail to receive 100% of Cycle 1 voruciclib doses will be replaced.

The data collected from subjects being replaced will be analyzed according to the analysis population(s) they belong to. Analysis population(s) are defined in Chapter 6.

### **3.1.5 Dose Modifications**

Details are provided in the Dose Modification Schedule in the study protocol (Section 4.8), which is intended as a guideline since the final decision about a dose reduction or whether to restart study medication is to be made by the Investigator. Variations from these recommendations may be warranted based on an Investigator's individual judgment in considering potential risks, benefits, and therapeutic alternatives available to each subject, and after discussion with the Medical Monitor.

### **3.1.6 Discontinuation of Voruciclib Administration**

Subjects may continue to receive voruciclib for up to 19 cycles (approximately 18 months). After this period, if there is continuing evidence of clinical benefit and acceptable toxicity as judged by the Investigator, following discussion with the Medical Monitor, the subject may be allowed to receive additional cycles. Subjects may discontinue voruciclib for reasons including the following:

- Documented progression of disease while receiving therapy
- Unacceptable AE(s) considered secondary to voruciclib despite appropriate therapy and/or dose modification
- Intercurrent illness that precludes continued study therapy
- Withdrawal of consent by the subject
- Changes in the subject's medical condition that render further administration of voruciclib unacceptable in the judgment of the Principal Investigator or sponsor
- Treatment of the disease with another therapeutic regimen
- Pregnancy or breastfeeding
- Substantial noncompliance with study procedures
- Termination of study by the sponsor

## 3.2 Study Centers

This is a multi-center study and will include approximately 10-16 sites in the United States (US).

## 3.3 Study Population

The study population consists of subjects with relapsed/refractory B cell malignancies, including Follicular lymphoma (FL), mantle cell lymphoma (MCL), marginal zone lymphoma (MZL), small lymphocytic lymphoma (SLL), chronic lymphocytic leukemia (CLL), and diffuse large B-cell lymphoma (DLBCL) or acute myeloid leukemia (AML).

Specific inclusion and exclusion criteria are specified in Sections 3.1 and 3.2, respectively, of the study protocol.

## 3.4 Study Treatment

Voruciclib will be administered once daily either daily continuously or intermittently on dosing days of either IS2w,2w or IS1w,3w, in 28-day cycles, with the first day of treatment designated as Day 1. For cohort 12 of voruciclib + venetoclax combination therapy, the dose of voruciclib will be 50 mg once every other day (QOD) on days 3, 5, 7, 9, 11, and 13 of Cycle 1, and on days 1, 3, 5, 7, 9, 11, and 13 of Cycle 2 and beyond.

Voruciclib is provided as 50 and 100 mg capsules and is to be taken orally on an empty stomach at least 1 hour prior to food or 2 hours after food at approximately the same time each day, on dosing days. It is recommended that voruciclib be taken in the morning. For combination voruciclib + venetoclax cohorts, subjects should take venetoclax with a meal and water, and then take voruciclib (malonate salt tablets) at least 2 hours later. A missed dose may be taken up to 12 hours after the usual time. After 12 hours the dose will be omitted.

## 3.5 Study Duration

The study consists of a screening period, a treatment period, and an End-of-Study (EOS) visit. Screening assessments are to be performed within 28 days of the first dose of study drug. Moreover, the treatment phase begins on the first day of study drug administration, continues through the last day of administration, and will be tracked by 28-day periods identified by a numerical cycle (e.g., Cycle 1, Cycle 2...). Response assessments will be performed according to the Schedule of Assessments ([Appendices 1, 2 and 3 of the protocol](#)). Finally, the EOS visit will occur 30 days from the last day of study drug administration (or prior to starting a new treatment if urgent treatment is required).

## 3.6 Randomization and Blinding

Not applicable.

### 3.7 Study Assessments

For the detailed schedule of expected events and study procedures to be conducted at each visit, please refer to Appendices 1, 2, and 3 (Schedule of Assessments), 4 (AML Response Criteria), 5 (CLL/SLL Response Criteria) and 6 (FL Response Criteria) in the protocol.

## 4. SAMPLE SIZE DETERMINATION

The MTD will be determined employing a standard 3 + 3 design. For voruciclib monotherapy, because enrollment will be conducted independently in subjects with AML and B-cell malignancies, within each disease group, dose and regimen changes will follow the 3 + 3 design, summarized below. Initially, 3 subjects will be enrolled at the lowest dose level in IS2w,2w in each disease group:

- If 0 of 3 subjects experience a DLT during Cycle 1, another 3 subjects will be enrolled at the next higher dose level.
- If > 1 of 3 subjects have a DLT during Cycle 1, this dose level will be declared as not safe, further dose escalation on the IS2w,2w regimen will not proceed, and IS1w,3w evaluating a less intensive dose regimen will be studied.
- If 1 of 3 subjects experiences a DLT during Cycle 1, an additional 3 subjects will be enrolled at the same dose level, with dose escalation permitted only if there are no additional DLTs.
- If > 1 of 3 subjects experience a DLT (in all but the lowest dose level) during Cycle 1, the next lower dose level within the IS will enroll an additional 3 subjects (for a total of 6 subjects).
  - If ≤ 1 of 6 subjects experience a DLT during Cycle 1, this dose level will be declared the MTD.
  - If > 1 of 6 subjects experience a DLT (in all but the lowest dose level) during Cycle 1, the next lower dose level within the IS will enroll an additional 3 subjects.\*

\*Within each disease group in a dose cohort, if the next lower dose regimen had previously enrolled 6 subjects, then the lower dose regimen will be declared the MTD.

For voruciclib + venetoclax combination therapy in AML, the same standard 3 + 3 design will be followed for voruciclib dose escalation on the IS2w,2w regimen.

At the start of Amendment 11, a total of 33 subjects have been enrolled in Cohorts 1, 2, 6a, 6b, 7a, 7b and 8a; the AML monotherapy expansion cohort enrolled 6 subjects. Assuming an average enrollment of 4 subjects per dose cohort for DLT evaluation, up to 12 subjects to be enrolled in the combination AML expansion cohort, and an additional 20% for early drop-outs due to non-evaluability after failure to complete Cycle 1 treatment for reasons other than AEs related to voruciclib, the total enrollment for initial dose/regimen escalation phase is estimated to be approximately 100 subjects for monotherapy (AML and B-cell malignancies), combination therapy (AML) and expansion cohorts.

## 5. STUDY ENDPOINTS

### 5.1 Efficacy Endpoints

#### 5.1.1 Primary Efficacy Endpoint

Not applicable.

#### 5.1.2 Secondary Efficacy Endpoints

Secondary efficacy endpoints (within each tumor type: AML and B cell malignancies) are as follows:

- Overall Response Rate (ORR), defined as the proportion of subjects who achieve a best overall response of
  - CR, CRi, or PR, with responses defined per 2008 International Workshop on CLL (IWCLL) guidelines,
  - CR or PR by 2014 Lugano criteria for non-Hodgkin lymphoma,
  - CR, CRi, CRMRD, MLFS by the 2017 ELN criteria for AML
- Estimates of the exposure and association with efficacy variables for voruciclib administered as monotherapy, and for voruciclib and venetoclax when administered in combination
- Duration of Response (DOR) defined as the time from first achieving a response to date of documented disease progression or death from any cause. Subjects who die due to any cause prior to progression will be censored. DOR will be calculated as follows for subjects who have a best overall response of CR/CRi or PR:

$$\text{DOR (months)} = (\text{Progression/Censoring Date} - \text{Response Start Date} + 1) / 30.4375$$

Subjects meeting at least one of the following criteria will be right-censored for DOR:

- death due to any cause prior to disease progression
- subsequent anticancer therapy without documented disease progression
- alive and without documented disease progression on or before the EOS visit

If a subject meets more than one of these criteria, then the scenario that occurs first will be used for the analysis. The progression or censoring date will be determined based on the conventions listed in Table 5-1.

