10.2. Study Endpoints

The primary study objectives are to determine the safety and tolerability and safe and mBED of voruciclib monotherapy in subjects with relapsed and/or refractory B-cell malignancies and AML and to determine the safety, tolerability and safe and mBED of voruciclib in combination with venetoclax in subjects with relapsed and/or refractory AML.

Safety will be assessed by AEs graded according to NCI CTCAE v5.0; laboratory safety tests including hematology (CBC), serum chemistry; physical examination; vital signs; ECOG performance status; and triplicate 12-lead ECG. If 2 or more of 6 subjects experience a DLT in a dose cohort, then the next lower dose will be the MTD.

The primary endpoint is:

- The incidence of AEs, including DLTs.

Secondary endpoints are:

- Efficacy endpoints within each tumor type:
 - a. Overall Response Rate (ORR), defined as the proportion of subjects who achieve a best overall response of
 - CR, CRi, or PR, with responses defined per 2008 International Workshop on CLL (IWCLL) guidelines,
 - CR or PR by 2014 Lugano criteria for non-Hodgkin lymphoma,
 - CR, CRi, CR_{MRD}, MLFS by the 2017 ELN criteria for AML
 - b. DOR defined as the time from first achieving a response to date of documented disease progression or death from any cause. Subjects who die due to any cause prior to progression will be censored
 - c. PFS defined as time from first dose of study drug to date of documented disease progression or death from any cause
 - d. Estimates of the exposure and association with efficacy and safety variables for voruciclib administered as monotherapy, and the PK of voruciclib and venetoclax when administered in combination

The exploratory endpoints are:

- a. Effects on biomarkers and functional activities of proteins in the apoptotic pathway
- b. Correlations of anti-tumor activity and baseline tumor characteristics

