10.6. Efficacy Analyses

For the Efficacy population, response to treatment will be tabulated with 95% exact binominal CIs.

The Kaplan-Meier method will be used to estimate PFS and DOR within subjects of the same tumor type. For PFS, subjects without documented progression will be censored at the date of last disease assessment.

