Stable disease	Absence of CR _{MRD} -, CR, CR _i , PR, MLFS; and criteria for PD not met	Period of stable disease should last at least 3 months

Table 18: European LeukemiaNet (ELN) Response Criteria in AML (Continued)

Category	Definition	Comment
Progressive disease (PD)*,†	
Evidence for an increase in bone marrow blast percentage and/or increase of absolute blast counts in the blood:
 
 >50% increase in marrow blasts over baseline (a minimum 15%-point increase is required in cases with <30% blasts at baseline; or persistent marrow blast percentage of >70% over at least 3 months; without at least a 100% improvement in ANC to an absolute level ($>0.5 \times 10^9/\text{L}$ [$500/\mu\text{L}$], and/or platelet count to $>50 \times 10^9/\text{L}$ [$50,000/\mu\text{L}$] non-transfused); or >50% increase in peripheral blasts ($\text{WBC} \times \% \text{ blasts}$) to $>25 \times 10^9/\text{L}$ ($>25,000/\mu\text{L}$) (in the absence of differentiation syndrome)†; or New extramedullary disease 	
Category mainly applies for older subject given low-intensity or single-agent “targeted therapies” in clinical trials
 
In general, at least 2 cycles of a novel agent should be administered
 
Some protocols may require blast increase in 2 consecutive marrow assessments at least 4 weeks apart; the date of progression should then be defined as of the first observation date
 
Some protocols may allow transient addition of hydroxyurea to lower blast counts
 
“Progressive disease” is usually accompanied by a decline in ANC and platelets and increased transfusion requirement and decline in performance status or increase in symptoms

Relapse		
Hematologic relapse (after $\text{CR}_{\text{MRD-}}$, CR , CR_i)	Bone marrow blasts $\geq 5\%$; or reappearance of blasts in the blood; or development of extramedullary disease	
Molecular relapse (after $\text{CR}_{\text{MRD-}}$)	If studied pretreatment, reoccurrence of MRD as assessed by RT-qPCR or by MFC	Test applied, sensitivity of the assay, and cutoff values used must be reported; analyses should be done in experienced laboratories (centralized diagnostics)

Abbreviations: ANC = absolute neutrophil count; IDH = isocitrate dehydrogenase; MFC = multiparameter flow cytometry; MLFS = morphologic leukemia-free state; MRD = minimal residual disease; RT-qPCR = quantitative reverse transcription polymerase chain reaction (assay); WBC = white blood cell.

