**Table 5-1: Date of Progression or Censoring for DOR**

| Situation                    | Date of progression or censoring                                   | Outcome |
|------------------------------|--|---------|
| Disease progression or death | Date of death or date of disease assessment (planned or unplanned) | Event   |

|  |  |          |
|--|--|----------|
|  | showing disease progression, whichever occurs first                          |          |
| Subsequent anticancer treatment started before the first disease progression | Date of last disease assessment prior to the subsequent anticancer treatment | Censored |
| Alive and without disease progression on or before the EOS visit             | Date of last disease assessment  | Censored |

- Progression-Free Survival (PFS) defined as time from first dose of study drug to date of documented disease progression or death due to any cause. PFS will be calculated as follows:

$$\text{PFS (months)} = (\text{Event/Censoring Date} - \text{Date of the First Dose} + 1) / 30.4375$$

PFS will be right-censored for subjects who met one or more of the following conditions:

- subsequent anticancer therapy in the absence of documented disease progression
- alive and without documented disease progression on or before the EOS visit

If a subject meets more than one of these conditions, then the scenario that occurs first will be used to determine PFS. The event or censoring date will be determined based on the conventions listed in Table 5-2:

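### Duration of response is defined with death both as an event and as censored, and the plan does not say whether AML relapse ends a response

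*SAP*

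**What the plan says.** **Death in DOR.** SAP 5.1.2 has DOR "defined as the time from first achieving a response to date of documented disease progression or death from any cause". The next sentence reads "Subjects who die due to any cause prior to progression will be censored", and the first item in the right-censoring list is "death due to any cause prior to disease progression". The same section then refers to Table 5-1 for the date. The first row of that table joins progression and death. Its date column opens "Date of death or date of disease assessment (planned or unplanned" and its outcome is an event. The other two rows cover new anticancer treatment and subjects alive without progression, so no row dates a censored death. SAP 8.6.2 repeats the definition without the censoring sentence. Protocol 10.2 contains both the definition ("DOR defined as the time from first achieving a response to date of documented disease progression or death from any cause") and the censoring sentence.

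**Relapse in AML.** In both documents the DOR and PFS events are documented disease progression or death. Protocol Appendix 4, Table 18, lists progressive disease and relapse as separate categories. Hematologic relapse, defined only after CR without MRD, CR or CRi, is marrow blasts of at least 5%, or "reappearance of blasts in the blood; or development of extramedullary disease". The main marrow criterion for progressive disease is a rise of more than 50% over baseline, and SAP 7.2 takes baseline as the last value before first dose.

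**PFS.** Protocol 10.6 says "For PFS, subjects without documented progression will be censored at the date of last disease assessment", and the synopsis says the same. Protocol 10.2 and SAP Table 5-2 count death as a PFS event.

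**Who enters DOR.** SAP 5.1.2 computes DOR for a best response of CR/CRi or PR. For AML, the same section counts CR, CRi, CR with MRD status and MLFS in ORR.

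**The concern.** Two programmers following this SAP could report different DOR medians from the same data, each with text to support the choice. The protocol cannot break the tie, because it contains the same contradiction, and SAP 10 declares no changes from the protocol. The study is open-label, so a rule chosen later would be chosen with outcomes visible.

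Death in response is a loss of response. If it is censored, Kaplan-Meier treats those subjects as if they would have gone on to the same later course as the survivors, and the median lengthens.

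Relapse is the usual way a leukemic remission ends. If a relapse is not recorded as an event, the response runs on until progressive disease or death, or is censored when new therapy starts. Protocol 10.1 reports the monotherapy cohorts as completed and the combination cohorts enroll AML only, so this gap applies to every subject still to be enrolled.

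**Working it through.** The documents give no target, event count or power for DOR, so there is no planned figure to reproduce. The check is a comparison of the text with two illustrations.

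**1. The death rule, place by place.**

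| Place | Death before progression |
|---|---|
| SAP 5.1.2, definition | ends DOR |
| SAP 5.1.2, next sentence | censored |
| SAP 5.1.2, first censoring bullet | censored |
| SAP Table 5-1, row 1 | event |
| SAP 8.6.2 | ends DOR; no censoring sentence |
| Protocol 10.2, definition | ends DOR |
| Protocol 10.2, next sentence | censored |

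**2. Size if the censoring text is followed.** Let λ be the constant total hazard of losing response and s the share of losses that are deaths without progression.

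- Deaths as events: median = ln 2 / λ.
- Deaths censored: only the hazard λ(1 − s) is counted, so the median tends to ln 2 / [λ(1 − s)].
- Ratio = 1/(1 − s).

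The documents do not give s. Over an assumed range:

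- s = 10%: 1/0.90 = 1.11
- s = 25%: 1/0.75 = 1.33
- s = 40%: 1/0.60 = 1.67

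Under Table 5-1 the ratio is 1.

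**3. The same effect by hand.** Take four hypothetical responders: progression at 2 months, death in response at 3, progression at 5, alive at 6.

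- Death as event: S(2) = 3/4 = 0.75; S(3) = 0.75 × 2/3 = 0.50; S(5) = 0.50 × 1/2 = 0.25. Median 3 months.
- Death censored: S(2) = 0.75; S(5) = 0.75 × 1/2 = 0.375. Median 5 months.

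**4. The relapse gap.** The marrow threshold for progressive disease is 1.5 × baseline. If baseline is under 30%, a rise of at least 15 points is also required. Hematologic relapse needs 5% at any baseline.

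| Pre-treatment marrow blasts | Progressive disease needs | Relapse needs |
|---|---|---|
| 20% | 35% (20 + 15) | ≥5% |
| 30% | >45% | ≥5% |
| 40% | >60% | ≥5% |
| 60% | >90% | ≥5% |

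A subject in CR from a 40% baseline who relapses at 30% marrow blasts has relapsed but does not meet this progression criterion. Unless another progressive-disease criterion is met (new extramedullary disease, or the peripheral-blast rule), the literal text records no event. If new therapy then starts, Table 5-1 censors the response at the last assessment before it. The table shows that the gap exists; it does not estimate the bias, because the documents give no relapse share.

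**The case against.** The strongest reply is that Table 5-1 governs. SAP 5.1.2 refers to it for the date, it has no row for a censored death, and SAP 8.6.2 drops the censoring sentence. If so, the death-related inflation is zero. That stands as a limit: a reader might infer that DOR is overstated as planned, and the documents do not support that, because the overstatement arises under only one of two stated rules. It does not remove the contradiction, since the censoring list is equally explicit and appears just above the table.

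A reader might also infer that the plan excludes relapse as an event. It does not say so. The whole ELN table is adopted, including its relapse section, response is determined by the investigator, and SAP 8.6.2.2 speaks of a median relapse time, which suggests that relapse was meant to count. That term is never defined or tied to the DOR event, so the rule is unspecified rather than an exclusion. The gap also concerns only relapses that meet no progressive-disease criterion at the same time.

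A third tempting reading is that PFS will censor deaths. Protocol 10.2 and SAP Table 5-2 make death an event, so what remains is loose wording in Protocol 10.6 and the synopsis.

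Finally, DOR should not be presented as driving decisions. It is one of several secondary endpoints, summarized descriptively, and the SAP calls the study exploratory. The combination dose criteria are DLTs, ORR and trough concentration.

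**Conclusion.** The concern holds as a contradiction and an omission. The DOR rule for death is stated both ways, so the endpoint is not computable consistently from the documents. Under the censoring reading the median is inflated by 1/(1 − s), which is 1.11 to 1.67 times for s from 10% to 40%. This rests on constant hazards and on shares that are assumed, not taken from the plan. Under Table 5-1 there is no such bias.

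Whether AML relapse ends a response is left unspecified. The literal reading biases DOR upward, by an amount that cannot be derived from the documents. The PFS point is a wording correction. No type I error, sample size, escalation rule or choice of minimum biologically effective dose depends on DOR.

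**What to change.** 1. Delete the censoring sentence in Protocol 10.2 and SAP 5.1.2 and the first DOR censoring bullet in the SAP. Keep Table 5-1, with death as an event.
2. In Protocol 10.6 and the synopsis, limit PFS censoring for lack of progression to subjects who are alive without progression, to match SAP Table 5-2.
3. For AML, define the DOR and PFS event as the earliest of Table 18 hematologic relapse (after CR without MRD, CR or CRi), progressive disease, or death.
4. Align the AML responder set for DOR (CR/CRi or PR in the SAP) with that for ORR (CR, CRi, CR with MRD status, MLFS). State how loss of response is dated for any MLFS or PR responders kept in DOR, since Table 18 defines no relapse for them.

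The cost is wording in both documents, best settled before database lock. Reported medians may be shorter.
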